11.3. ANALYSIS AND EVALUATION

11.3.1. Statistical Analysis

Evaluation elements are defined as the questions on the CRF/eCRF. The SAP lists all evaluation elements and secondary elements which will be based on calculations between two or more evaluation elements.

All quantitative variables, including those based on calculations (secondary elements), will be analyzed with a case summary evaluation before the detailed characteristics and parameters can be evaluated. A case summary contains a listing of the number of valid cases/values, missing cases/values (if any) and total cases/values in the specific analysis. In general, as central position parameter for quantitative variables the mean, median and mode will be analyzed. As variation parameter the standard deviation, 95% confidence interval of the mean, interquartile range and range (based on maximum and minimum) will be calculated. All quantitative variables will be assessed for normality using the Shapiro-Wilk test. For optional visualization of quantitative variables, box-and-whisker plots will be used. Additional analyses like skewness and kurtosis measures or standard errors also are optional.

All qualitative variables, including those based on summaries (secondary elements), will be analyzed listing the proportions, frequencies, column and row totals, and missing proportion, if any.

The SAP reflects this approach and specifies the variables characteristics (quantitative or qualitative) in detail together with the related analysis strategy. This also includes calculation and summaries based on primary elements and the required analysis.

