11.3.2. Primary Analysis / Endpoint

The objective of the clinical investigation is to demonstrate the non-inferiority (equal or better) of the ASES Shoulder Score in relationship to the officially cleared indications in comparison to respective clinical outcome data in the scientific literature.

[figure not shown]
Data collection of ASES Shoulder Score will start pre-operatively and will be collected according to schedule in Table 1. This will be repeated annually in all subjects who have the prosthesis with full or partial implant survival (including all subjects without removal of all endo-prosthesis components).

The 24 months post-operative results for subjects implanted with ReUnion RSA System will be compared to a historical group and results reported by respective clinical outcome data in the scientific literature. The benchmark sources and values will serve as the control group for the ReUnion RSA System subjects.

Higher ASES Shoulder Score results are linked to better subject results and vice versa.

The clinical investigation endpoint is non-inferiority to the control, meaning the clinical investigation result should be equal or better than the control. In this clinical investigation, an equal or better ASES score result means equal or more (\geq). As only results from samples will be captured, results are mostly estimates of the true population parameter. These estimates vary by a certain area, where it is expected that the true population parameter falls within. Based on this, it is required to specify a lower limit for the acceptable difference or zone of indifference, denoted as $-\theta$.

Hypotheses are developed to allow for a comparison of the 24 months post-operative ASES score effectiveness / performance between the two underlying populations. The 24 months post-operative ASES Shoulder Score is the primary endpoint of this clinical investigation. Hypothesis tests will be one-sided with a significance level α of 5%.

Hypothesis	Equations	Interpretation
Null (H_0)	$A - B < -\theta$	Central tendency of A is inferior to the central tendency of B.
	ReUnion RSA System – Control (Benchmark) $< -\theta$	
Alternative (H_1)	$A - B \geq -\theta$	Central tendency of A is non-inferior to the central tendency of B.
	ReUnion RSA System – Control (Benchmark) $\geq -\theta$	
		
Possible Evidence (p)	Possible Decisions	Possible Conclusions – ASES score

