p-value $> \alpha$ (0.05)	Fail to reject null hypothesis (H_0)	ReUnion RSA System $<$ Control (Benchmark) Insufficient evidence to reject the null hypothesis ($H_0: A - B < -\theta$) at the pre-determined significance level of 5%.
p-value $\leq \alpha$ (0.05)	Reject null hypothesis (H_1)	ReUnion RSA System \geq Control (Benchmark) Sufficient evidence to reject the null hypothesis ($H_0: A - B < -\theta$) at the pre-determined significance level of 5%.

To test non-inferiority, the 24 months mean ASES Shoulder Score result of the ReUnion RSA System group will be compared to the mean estimate of the control group (71.27 points).

To be able to identify an acceptable difference or zone of indifference ($-\theta$), the pooled standard deviation of the ASES Shoulder Score result at 24 months post-operative in the control group (Benchmark) was used as lower limit (pooled standard deviation of control is 19.40 points).

The lower maximum acceptable difference ($-\theta$) is 51.87 points (mean of control - θ or $71.27 - 19.40 = 51.87$ points).

Based on the underlying distribution of the data and the result of the normality assessment, either the parametric one-sample t-test or the non-parametric one-sample sign test will be used to compare the 24 months post-operative ASES Shoulder Score results of the ReUnion RSA System against the value of 51.87 points.

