p-value > $\alpha$ (0.05)	Fail to reject null hypothesis ( $H_0$ )	ReUnion RSA System < Control (Benchmark) Insufficient evidence to reject the null hypothesis ( $H_0: A - B < -\theta$ ) at the pre-determined significance level of 5%.
p-value $\leq \alpha$ (0.05)	Reject null hypothesis ( $H_1$ )	ReUnion RSA System $\geq$ Control (Benchmark) Sufficient evidence to reject the null hypothesis ( $H_0: A - B < -\theta$ ) at the pre-determined significance level of 5%.

Table 3.1.1: Research Goal and Hypothesis (Primary Endpoint)

To test non-inferiority, the 24 months mean ASES Shoulder Score result of the ReUnion RSA System group will be compared to the mean estimate of the control group (71.27 points).

To be able to identify an acceptable difference or zone of indifference ( $-\theta$ ), the pooled standard deviation of the ASES Shoulder Score result at 24 months postoperative in the control group (Benchmark) was used as lower limit (pooled standard deviation of control is 19.40 points). The lower maximum acceptable difference ( $-\theta$ ) is 51.87 points (mean of control -  $\theta$  or 71.27 – 19.40 = 51.87 points).

Based on the underlying distribution of the data and the result of the normality assessment, either the parametric one-sample t-test or the non-parametric one-sample sign test will be used to compare the 24 months postoperative ASES Shoulder Score results of the ReUnion RSA System against the value of 51.87 points.

The analysis of the primary endpoint / objective will be conducted when all subjects have completed the 24 months postoperative visit including the ASES Shoulder Score.

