#### 4.10. ASSUMPTIONS

In case of deviation from assumptions (e.g. normality), non-parametric methods will be used for analysis. No transformation of such data will be performed.

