## 6.6. ANALYSIS OF CI ENDPOINTS

Evaluation Variable / Question	Level of Measurement	Analysis Plan					
Endpoints – Primary Endpoint							
Use variable Total ASES Score 24 Months [points]:							
Based on the underlying distribution of the data and the result of the normality assessment, either the parametric one-sample t-test or the non-parametric one-sample sign test will be used to compare the 24 months postoperative ASES Shoulder Score results of the ReUnion RSA group against the lower maximum acceptable difference ( $-\theta$ ) of 51.87 points.							
The analysis of the primary endpoint will be part of the final report.							

Table 6.6.1: Endpoints – Primary Endpoint Tables List

Evaluation Variable / Question	Level of Measurement	Recode and Analysis Plan	Inclusion		
Adverse Events – Time to (earliest) Device-Related Adverse Event / Incident			IR	FR	N/A
Creation of variable Difference between Date of Surgery [dd.mm.yyyy] and Date of First Device Related Adverse Event [dd.mm.yyyy] in [ ] days [ ] (Variable(s): VISITDT; AEONSTD)	Quantitative, ratio	Case summary with number and percentage of valid cases/values, missing cases/values (if any) and total cases/values. Mean, median, interquartile range, maximum, minimum, standard deviation, 95% confidence interval for mean, Shapiro-Wilk Test.		X	
Creation of variable Difference between Date of Surgery [dd.mm.yyyy] and Date of “most recent” Visit [dd.mm.yyyy] in [ ] days [ ] (Variable(s): VISITDT)	Quantitative, ratio	N/A (Analyzed above), used for survivorship		X	
Create new variable “Grouping variable – First Device Related Adverse Event” (Variable(s): AEONSTD)	Qualitative, nominal	- censored = survivors - events = first (earliest) Device Related Adverse Event		X	

Create new variable “Combined Time – First Device Related Adverse Event” (Variable(s): AEONSTDT)	Quantitative, ratio	- Use time between surgery and “most recent” visit for surviving subjects - Use time between surgery and first device related adverse event for subjects with device related adverse event	X	

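### The normality result decides whether the primary non-inferiority claim concerns the mean or the median; under left skew near 51.87, false non-inferiority for the mean can exceed 5%

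*Protocol*

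**What the plan says.** Protocol 11.3.2 describes the target in two ways. The text says that the 24-month "mean ASES Shoulder Score result of the ReUnion RSA System group will be compared to the mean estimate of the control group", given as 71.27 points. The hypothesis table names no parameter; its null reads "Central tendency of A is inferior to the central tendency of B". The limit is the benchmark mean less an average standard deviation: 71.27 - 19.40 = 51.87.

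The test then depends on the data. Protocol 11.3.1 states "All quantitative variables will be assessed for normality using the Shapiro-Wilk test", and 11.3.2 follows with "either the parametric one-sample t-test or the non-parametric one-sample sign test will be used to compare" the scores with 51.87. SAP 3.1.1 repeats the choice, and SAP 6.6 applies the same two tests "against the lower maximum acceptable difference" of 51.87. SAP 4.10 makes the switch a rule and excludes transformation: "In case of deviation from assumptions (e.g. normality), non-parametric methods will be used for analysis".

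The hypothesis is tested one-sided at 5%. No Shapiro-Wilk cut-off is tied to the switch; Protocol 11 and SAP 4.7 only set p ≤ 0.05 in general. No sensitivity analysis with the other test is planned.

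**The concern.** A one-sample t-test and a one-sample sign test against the same number answer different questions unless the distribution is symmetric. The first asks whether the mean exceeds 51.87, the second whether more than half of subjects do. The margin was derived for a mean; the documents give no median-based margin.

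The switch also tends to work in the unsafe direction. A subgroup of very poor results makes Shapiro-Wilk more likely to reject, and the sign test then ignores how poor those results are. Such a subgroup is foreseeable: the trial mixes four indications, including failed arthroplasty, and the benchmark means range from 40.8 (a revision series) to 86.7. At stake is the pass/fail decision on the only hypothesis with a stated decision rule.

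**Working it through.** **The plan's own figure.** Protocol 11.1 gives 80.3% power at n = 10 for mean 71.27, SD 19.40 and limit 51.87. The effect size is (71.27 - 51.87)/19.40 = 1. A noncentral t with 9 degrees of freedom and two-sided 5% gives 80.31%, so the figure reproduces for the t-test. At the one-sided 5% of 11.3.2 it would be 89.8%.

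**Sample sizes.** 80 enrolled with 56% drop-out leaves 80 × 0.44 = 35.2, so n = 35; n = 80 is full retention.

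**Why the sign test can pass.** At one-sided 5% the exact sign test needs at least 23 of 35 or 48 of 80 scores above 51.87. Suppose 20% of subjects are failures, N(20, 8), and the rest have SD 12. For an overall mean of 51.87 the main-group mean must be (51.87 - 0.20 × 20)/0.80 = 59.84. The share above 51.87 is then 0.80 × Φ((59.84 - 51.87)/12) = 0.80 × Φ(0.664) ≈ 0.60. With a true share of 0.60 the sign test passes with probability 30.6% at n = 35 and 54.8% at n = 80, although the mean is exactly at the limit.

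**The planned two-step rule, simulated.** Shapiro-Wilk p ≤ 0.05 (assumed cut-off) leads to the sign test; otherwise a one-sided 5% t-test is used. There were 10,000 replicates per cell (standard error at most 0.5 points), with a true mean of 51.87. In the mixtures, scores are held to 0-100 (assumed range) and failures are N(20, 8).

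| Assumed shape | n = 35 | n = 80 |
|---|---|---|
| 20% failures, main SD 12 | 26.6% | 51.7% |
| 20% failures, main SD 15 | 12.4% | 24.9% |
| 20% failures, main SD 19.4 | 6.6% | 10.0% |
| 15% failures, main SD 12 | 18.5% | 36.6% |
| 15% failures, main SD 15 | 9.3% | 16.1% |
| 15% failures, main SD 19.4 | 5.9% | 7.7% |
| Beta (mean 71.27, SD 19.4, skewness -0.68) shifted down 19.4 | 16.1% | 26.9% |
| Near-symmetric beta on 0-100, SD 19.4-28 | 5.2-6.0% (both n) | |

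The t-test alone gives 4.9-6.4% in the mixtures, 6.4% / 5.6% in the shifted beta, which has 0.9% of scores below 0, and 4.7-5.3% in the near-symmetric beta.

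**Other left-skewed shapes** (reflected gamma, SD 19.4, 20,000 replicates), n = 35 / n = 80: skewness -0.5 gives 8.3% / 11.5%; -1.0 gives 16.8% / 30.7%; -1.5 gives 30.7% / 55.0%. At one-sided 2.5%, skewness -1.0 still gives 9.8% / 17.2%.

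**Below the limit.** With 20% failures and main SD 12, a true mean of 50 passes in 10.4% / 18.2% of trials (t-test 1.9% / 0.8%). In that shape at a true mean of 51.87, 2.2% / 11.2% of trials pass with an observed mean below 51.87.

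**How likely the switch is.** A beta on 0-100 with the planning mean and SD has Shapiro-Wilk rejecting in 57% of trials at n = 35 and 97% at n = 80. Five of the 15 benchmark rows with an SD (6a, 10, 15a, 17a, 17b) have mean + SD above 100. If 100 is the maximum, those scores are unlikely to be near normal.

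**The case against.** The strongest reply is that the size depends on assumed shapes. This stands. A failing subgroup alone is not enough: with 15-20% failures centred at 35 (SD 10), the rule gives only 4-6% at n = 35 and 4-7% at n = 80. With 10% failures at 20 it gives 6-12% and 6-21%; with 5%, 6-8% and 5-11%. The highest rates need failures that are very poor, fairly common and well separated. Right skew reverses the effect: skewness +1 gives 2.7% / 0.7%.

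Practical reach is also limited. The risk needs a true mean about 19 points below the benchmark, and 24 of the 25 benchmark means exceed 51.87. At the planning mean the switch rule passes at least 99.8% of trials at n = 35 or more. At n = 10 almost none of the excess comes from the switch, because the sign test needs 9 of 10 above the limit; but the plan describes no separate test per indication.

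Finally, both tests and the trigger are pre-specified, the hypothesis table's wording could cover a median, and Protocol 11.3.1 and SAP 6.5 report the mean with its 95% CI and the median regardless. A reader could see a poor mean. That does not settle which parameter carries the claim, and the formal decision could still rest on the median.

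**Conclusion.** The concern holds. The parameter is not fixed; this follows from the text and needs no simulation. The consequence is conditional on left skew and a true mean near 51.87. Over the failure mixtures tabulated, false non-inferiority for the mean is 6-27% at n = 35 and 8-52% at n = 80, the upper ends being the worst of those shapes. It stays near 5-6% for near-symmetric scores. Because the two tests concern different parameters, the excess in the tabulated left-skewed shapes grows with n, so better retention makes it worse. The rates rest on the assumed shapes, a 0-100 range in the bounded ones, and a Shapiro-Wilk cut-off of 0.05. No power loss is claimed: at n = 10 and the planning values, the two-step rule at one-sided 5% keeps 88% (normal) or 80% (skewed beta). The point should be corrected before the 24-month analysis.

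**What to change.** In Protocol 11.3.2 and SAP 3.1.1 and 6.6:

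- State the hypotheses in terms of the mean.
- Make the one-sample t-test against 51.87 the only primary test whatever Shapiro-Wilk shows, reported with the one-sided 95% lower bound (the lower end of a two-sided 90% CI) that matches the one-sided 5% test.
- Add a bootstrap lower bound for the mean as a sensitivity analysis.
- Report the median and sign test descriptively only.

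In SAP 4.10, except the primary endpoint from the switch to non-parametric methods.

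The cost is one or two sentences in each section, with no data or patient cost. The downside is a small excess of the t-test over 5% under left skew: about 6% in the main shapes above, and up to 8.1% at n = 35 and 7.3% at n = 80 under the strongest skew tried (-1.5), where the planned switch gives 30.7% and 55.0%.

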11.3.3. Secondary Endpoints

The incidence of device-related AEs and implant survivorship will be assessed up to 10 years after the index procedure and monitored through collection and analyses. These analyses will be part of the annual and final reports.

Furthermore, time to (earliest) device-related AEs will be analyzed as well. For analysis of the time to the (earliest) device-related AEs as well as the time to secondary procedure (revision, removal, reoperation), the Kaplan-Meier method will be used. The time between surgery and the last available assessment will be used together with the time between date of surgery and the date of secondary procedure. Considered variables, the level of measurement and the planned analysis steps are listed in detail in the SAP.

11.3.4. Additional Analyses

Additional analyses are outlined in the subsequent sections. Analysis details (variables, level of measurement, planned steps) are listed in-depth in the SAP.

- **Mortality**

For analysis of the time to death or mortality, the Kaplan-Meier method will be used. The times between surgery and the last available assessment will be used together with the times between date of surgery and the date of death. This analysis will be part of the annual and final reports.

- **Total ASES Shoulder Score – Within subject changes by visit**

The within subject score changes of the ASES Shoulder Score from visit to visit will be analyzed to help identify the changes on the subject level. This analysis will be part of the annual and final reports.

11.4. MISSING DATA / SAP DEVIATIONS

The intent is to collect as complete a dataset as possible. Nevertheless, in some situations missing data cannot be avoided. The reports and tables therefore will show the number and percentage of missing cases for each analyzed variable in relation to the enrolled cases for each post-operative assessment.

Any deviations from the SAP will be listed in the annual or final reports.

11.5. REPORTS

11.5.1. Interim Analysis and Reports

Interim analyses will be performed on a yearly basis. The progress of the clinical investigation will be reported together with the interim results on the variable level according to the analysis plan.

The analysis of the primary endpoint will be part of the related interim / annual report when all subjects have completed the 24 months post-operative including the ASES Shoulder Score.

11.5.2. Final Analysis and Reports

The full final report with complete analysis including progress and conduct reporting will be created at the end of this clinical investigation.

12. Clinical Investigation Plan Deviations

A CIP deviation is a departure from the approved CIP that is not implemented or intended as a systemic change. All CIP deviations are recorded and reported to each site's IRB in accordance with the respective site's IRB policies.

13. Adverse Events

As this CIP is being carried out to satisfy the post-market requirements to support safety and efficacy/performance according to the European Medical Device Regulation (EU MDR), categorization and definition of device-related adverse events will follow the guidelines outlined in the EU MDR as “incident” reporting.

13.1. DEFINITIONS

- **An Adverse Device Effect (ADE)** is defined as any untoward or unintended response to the clinical investigation treatment; and/or a medical response which may have a causal relationship to the treatment.
- **An Incident** is defined as any malfunction or deterioration in the characteristics or performance of a device made available on the market, including use-error due to ergonomic features, as well as any inadequacy in the information supplied by the manufacturer and any undesirable side-effect.
- **A Serious Adverse Device Effect (SADE)** is defined as any ADE that results in consequences characteristic of a SAE or might lead to the consequences if suitable action or intervention is not taken; causes considerable interference with the subject's usual activities and may be incapacitating or life-threatening, including those events resulting in a subject's disability or permanent damage, or required intervention to prevent disability or permanent damage; results in a life-threatening illness or injury; and/or results in death (fatal).
- **A Serious Incident** is defined as any incident that directly or indirectly led, might have led or might lead to any of the following:
 - the death of a patient, user or other person;
 - the temporary or permanent serious deterioration of a patient's, user's or other person's state of health;
 - a serious public health threat
- **An Unanticipated Adverse Device Effect (UADE)** is defined as an AE not described in the informed consent, CIP or device labeling which has resulted in any of the consequences of a SAE or which might have led to any of the consequences of a SAE if suitable action had not been taken, intervention had not occurred, or if circumstances had been less opportune.

13.2. ADVERSE EVENT SEVERITY

The severity of all AEs is assessed by the Investigator utilizing the following categories:

- **Mild:** The AE is transient and easily tolerated by the subject.
- **Moderate:** The AE causes the subject discomfort and interrupts the subject's usual activities.
- **Severe:** The AE causes considerable interference with the subject's usual activities and may be incapacitating or life-threatening, including those events resulting in a subject's disability or permanent damage, and/or required intervention to prevent permanent disability or damage.
- **Life-Threatening:** The AE results in a life-threatening illness or injury.
- **Fatal:** The AE results in death.

13.3. RELATIONSHIP TO THE DEVICE

Only events considered possibly, probably or definitely related to the device will be captured for this clinical investigation.

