8.2. SECONDARY ENDPOINT

In addition to the principal endpoint, information on the following outcomes will be assessed up to 10 years after the index procedure:

Safety: Incidence of device-related intra-operative and post-operative AEs

Efficacy/Performance: Implant survivorship will be monitored

9. Selection of Clinical Investigation Population

Subjects participating in this clinical investigation will be recruited from the investigator's standard subject population, where all patients presenting for primary or revision total shoulder replacement will be evaluated for clinical investigation participation based on the eligibility criteria listed below.

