13.5. FORESEEABLE ADEs, SADEs and INCIDENTS

ADEs, SADEs and incidents which may be expected as part of the surgical intervention include:

- *Perioperative complications*
 - Malpositioning of the humeral or glenoidal component
 - Oversizing of implant components
 - Undersizing of implant components
 - Intraoperative fracture of the humerus or glenoid
 - Humeral cement leakage, if applicable
 - Nerve injury, mild (minor motor or sensory loss, or spontaneous recovery)
 - Nerve injury, severe (significant motor or sensory loss or requiring surgical revision)
 - Vessel injury
 - Tendon injury
 - Wound complications (e.g. hematoma, wound healing disturbances)
 - Superficial infection
 - Deep infection
 - Deep vein thrombosis
 - Pulmonary embolism
- *Complications in the follow-up period*
 - Implant dislocation
 - Other subluxation or instability, symptomatic
 - Implant component dissociation, humeral cup from humeral stem
 - Implant component dissociation, humeral insert from humeral cup
 - Implant component dissociation, glenosphere from baseplate
 - Implant fretting or crevice corrosion
 - Implant breakage/wear, humeral or glenoidal
 - Implant loosening, humeral
 - Implant loosening, glenoidal with or without screw breakage
 - Radiographic lucency, humeral or glenoidal
 - Pain related to the implant, severe
 - Late infection (e.g. hematogenous or protracted)

- Periprosthetic fracture of the humerus or glenoid
- Stress fracture of the acromion or the scapular neck
- Stress fracture of the coracoid
- Scapular notching, asymptomatic or symptomatic
- Stiffness
- Heterotopic ossification, asymptomatic or symptomatic
- Healing disturbances of subscapularis tenotomy, if applicable
- Non-union of lesser tuberosity osteotomy, if applicable
- Malunion of lesser tuberosity osteotomy, if applicable

14. Reoperations

Reoperations and reason(s) for reoperations will be collected throughout the course of the clinical investigation. A reoperation may include but not limited to irrigation and debridement, revision surgery and/or implant removal.

15. Ethics

This clinical investigation is to be conducted according to International Conference of Harmonisation of Good Clinical Practice (ICH-GCP), applicable regulations, institutional research policies and procedures, Declaration of Helsinki and in compliance with the CIP. Investigators will be trained on the clinical investigation devices and surgical techniques prior to implanting clinical investigation subjects.

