15.1. INSTITUTION REVIEW BOARD (IRB)

IRB approval will be obtained at each of the investigational sites prior to enrolling clinical investigation subjects at that site. In addition, any SAEs and UADEs that meet the reporting criteria of the IRB, will be reported to the IRB. During the clinical investigation, the Investigator should promptly provide written reports to the IRB of any changes that affect the conduct of the clinical investigation and/or increase risk to the subjects, unless otherwise submitted by the Sponsor.

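### The protocol captures only device-related events, but defines and lists adverse device effects by treatment and surgery, and the SAP holds no relationship variable, so the safety endpoint can undercount listed events

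*Protocol*

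**What the plan says.** The capture rule is in protocol section 13.3: "Only events considered possibly, probably or definitely related to the device will be captured for this clinical investigation". It names no assessor, gives no criteria for the three grades, and does not say whether an event due to the procedure alone counts.

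Two neighbouring sections use a wider frame. Section 13.1 defines an ADE as "any untoward or unintended response to the clinical investigation treatment; and/or a medical response which may have a causal relationship to the treatment", and section 10.2 describes the treatment as placement of the system. Section 13.5 opens its list with "ADEs, SADEs and incidents which may be expected as part of the surgical intervention include". Its perioperative part includes two grades of nerve injury, vessel and tendon injury, wound complications, superficial and deep infection, DVT and PE.

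The safety endpoint in section 8.2 reads "Safety: Incidence of device-related intra-operative and post-operative AEs". Protocol 11.3.3 and SAP 3.1.2 add a Kaplan-Meier analysis of time to the earliest such event, detailed in SAP Table 6.6.2.

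The opening text of protocol section 11 says that the SAP lists every variable of the investigation. SAP Table 6.1.1 covers timing, event, description, unanticipated status, severity, action, resolution, outcome, and counts by site and by subject. Its event variable is already labelled device-related, and no field holds the relationship.

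**The concern.** The decision on relatedness comes before the record. If a site judges a listed event to be due to the operation and not the implant, section 13.3 tells it to enter nothing. Another site can enter the same event because 13.5 names it as an ADE, a serious adverse device effect (SADE) or an incident. Both follow the plan, and the reported incidence differs.

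This is the only safety endpoint, and safety is half of the stated objective. The study has 4 to 7 sites, unblinded investigators and no described adjudication. Because neither the grade nor the events judged unrelated are in the listed data, no sensitivity analysis on attribution can be run afterwards. In the time-to-event analysis, a subject whose event was not entered is treated as a survivor and censored at the most recent visit.

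**Working it through.** The documents state no figure to reproduce. The check is a comparison of passages, followed by an illustration on assumed inputs.

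**Step 1. What each passage turns on**

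| Place | Turns on | A PE judged due to surgery only |
|---|---|---|
| Protocol 13.1, ADE | Treatment | Is an ADE |
| Protocol 13.1, SADE | An ADE with serious consequences | Is a SADE if serious |
| Protocol 13.4 | SADE, unanticipated effect or serious incident | Sponsor notified within 48 hours |
| Protocol 13.5 | Surgical intervention | Listed by name |
| Protocol 13.3 | Device | Not captured |
| SAP Table 6.1.1 | Event already labelled device-related | No record, no grade |

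The first four rows and the last two give different answers for the same event.

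**Step 2. How much of the list is exposed.** The perioperative part of 13.5 has 14 items. Five concern the implant or its placement directly: malpositioning, oversizing, undersizing, intraoperative fracture and cement leakage. The other 14 − 5 = 9 can plausibly be put down to surgery: two nerve grades, vessel, tendon, wound, superficial infection, deep infection, DVT and PE. This split is a reading of the list, not a classification made by the plan.

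**Step 3. Which of these have a second route into the data**

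- Reoperations are collected with reasons and no stated relatedness filter (protocol 14). The reason codes in SAP Table 6.1.2 include wound complication, infection and nerve palsy.
- Deaths are documented (protocol 9.3) and analysed (SAP 6.7.2).
- Radiographic findings are tabulated whatever their cause (SAP Tables 6.3.3 and 6.5.4).

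What remains is nerve, vessel, tendon, wound and infection events without reoperation, plus DVT and non-fatal PE.

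**Step 4. Illustration.** Let N = 80 (protocol synopsis). Let p be the true risk of a class of listed events and c the share judged device-related. Both p and c are assumed. With at most one event per subject and independent subjects:

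- expected captured events = N × p × c
- probability that at least one is captured = 1 − (1 − p × c)^N

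For p = 5% and c = 50%: 80 × 0.05 × 0.5 = 2.0 events, and 1 − 0.975^80 = 0.87.

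| p | c = 100% | 75% | 50% | 25% | 0% |
|---|---|---|---|---|---|
| 2% | 1.6 (0.80) | 1.2 (0.70) | 0.8 (0.55) | 0.4 (0.33) | 0 (0) |
| 5% | 4.0 (0.98) | 3.0 (0.95) | 2.0 (0.87) | 1.0 (0.63) | 0 (0) |
| 10% | 8.0 (>0.99) | 6.0 (>0.99) | 4.0 (0.98) | 2.0 (0.87) | 0 (0) |

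Cells show expected captured events, with the probability of at least one in brackets. In the first column nothing is lost.

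**The case against.** The strongest reply is that the endpoint is worded as device-related events throughout, so leaving out events truly unrelated to the device is a declared scope choice in a post-market, standard-of-care study. That stands: such omissions do not undercount the endpoint. The shortfall is against the 13.1 definition and the 13.5 list, and in events that are possibly related but were not judged so.

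Second, the passages can be read together. The threshold starts at possibly related, 13.5 itself labels the events as ADEs, SADEs or incidents, and the incident definition in 13.1 covers any undesirable side-effect. A site reading them so would capture everything. This stands as a possible reading, but nothing in 13.3 requires it.

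Some stronger readings are tempting and are not supported:

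- A reader might infer that 13.3 gives the decision to the operating surgeon. It names nobody. That the site investigator assesses adverse events is an inference from sections 13.2 and 17.
- A reader might see section 15.1 ("any SAEs and UADEs that meet the reporting criteria of the IRB, will be reported to the IRB") as a further contradiction. It is a separate duty from site to IRB and does not govern the study database.
- A reader might conclude that uncaptured events leave no trace and can never be reviewed. Step 3 shows other routes for some of them, and medical records remain. Section 17 monitoring compares completed forms with those records, although it is not expressly directed at events that were never entered.
- A reader might say that sites cannot be compared. The SAP plans only descriptive counts by site, so little rests on such a comparison.

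**Conclusion.** The point holds as an inconsistency that can lead to undercounting, not as a demonstrated undercount. Sections 13.1, 13.3 and 13.5 give different answers for procedure-related events and must be reconciled. The 48-hour notification in 13.4 is affected because a SADE is built on the treatment-based ADE definition. SAP Table 6.1.1 cannot show how attribution was made.

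The size is unknown. The documents give neither an event rate nor an attribution rate, and the gap is zero if every listed event is treated as at least possibly related. A reader might put the swing at 5 to 15 percentage points, by assuming 4 to 12 of 80 subjects affected (4/80 = 5%, 12/80 = 15%). That rests on an assumed rate, on attribution of 100% under one reading and 0% under the other, and on those subjects having no other captured event. It should not be quoted as an estimate.

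The primary ASES endpoint is untouched. This is a change that should be made, chiefly because it is cheap and protects the only safety endpoint.

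**What to change.** 1. In protocol 13.3, require that every event on the 13.5 list is recorded regardless of attribution, with two grades (relationship to device, relationship to procedure: none, possible, probable, definite) and a named assessor.
2. Align the ADE wording in 13.1 with this rule, so that definition, notification and capture use the same frame.
3. Keep the secondary endpoint as device-related events, now derived from the recorded device grade.
4. In SAP 6.1, add the two relationship variables and one table of all listed events regardless of attribution.

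Reoperations and deaths need no new rule, since both are already collected. The cost is protocol wording, the added form fields and one table. The downside is that sites enter some additional perioperative events. No visit or procedure is added.
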